#### 7.3.12 Home Healthcare

Subjects receiving peritoneal dialysis may not have to be seen routinely by the investigator at the clinical site on a weekly basis. These subjects will be required to be seen in the clinic every 2 weeks, including the week prior to the monthly dosing titration visit and those visits where central laboratory samples are collected, at a minimum during the trial. The investigator may utilize their site staff or a qualified home healthcare service provider to conduct the procedures required for remaining weekly study visits, subject to the investigator's direction and oversight.

## 7.4 Biomarker Development

Biomarkers are objectively measured and evaluated indicators of normal biologic processes, pathogenic processes, or pharmacologic responses to a therapeutic intervention. Biomarker development can be useful in developing markers to identify disease subtypes, guide therapy, and/or predict disease severity.

#### CONFIDENTIAL

Page 53 of 79

**AMGEN** 

Page 55

Amgen may attempt to develop test(s) designed to identify subjects most likely to respond positively or negatively to cinacalcet.

#### **Blood Samples**

Blood samples are to be collected for biomarker development at the following time points: day 1 and EOIP visit (week 28).

# 7.5 Sample Storage and Destruction

Any blood or biomarker sample collected according to the Schedule of Assessments (Table 4) can be analyzed for any of the tests outlined in the protocol and for any tests necessary to minimize risks to study subjects. This includes testing to ensure analytical methods produce reliable and valid data throughout the course of the study. This can also include, but is not limited to, investigation of unexpected results, incurred sample reanalysis, and analyses for method transfer and comparability.

All samples and associated results will be coded prior to being shipped from the site for analysis or storage. Samples will be tracked using a unique identifier that is assigned to the samples for the study. Results are stored in a secure database to ensure confidentiality.

If permitted by local regulations and informed consent is provided by the subject's legally acceptable representative(s), Amgen can do additional testing on remaining samples (ie, residual and back-up) to investigate and better understand the CKD and SHPT, the dose response and/or prediction of response to cinacalcet, and characterize aspects of the molecule (eg, mechanism of action/target, metabolites). Results from this analysis are to be documented and maintained, but are not necessarily reported as part of this study. Samples can be retained for up to 20 years.

Since the evaluations are not expected to benefit the subject directly or to alter the treatment course, the results of pharmacogenetic, biomarker development, or other exploratory studies are not placed in the subject's medical record and are not to be made available to the subject, members of the family, the personal physician, or other third parties, except as specified in the informed consent.

The subject retains the right to request that the sample material be destroyed by contacting the investigator. Following the request from the subject, the investigator is to provide the sponsor with the required study and subject number so that any remaining blood samples and any other components from the cells can be located and destroyed. Samples will be destroyed once all protocol-defined procedures are completed.

Page 55 of 79

However, information collected from samples prior to the request for destruction, will be retained by Amgen.

The sponsor is the exclusive owner of any data, discoveries, or derivative materials from the sample materials and is responsible for the destruction of the sample(s) at the request of the subject through the investigator, at the end of the storage period, or as appropriate (eg, the scientific rationale for experimentation with a certain sample type no longer justifies keeping the sample). If a commercial product is developed from this research project, the sponsor owns the commercial product. The subject has no commercial rights to such product and has no commercial rights to the data, information, discoveries, or derivative materials gained or produced from the sample. See Section 11.3 for subject confidentiality.

8. WITHDRAWAL FROM TREATMENT, PROCEDURES, AND STUDY

Subjects have the right to withdraw from the study at any time and for any reason without prejudice to their future medical care by the physician or at the institution.

Subjects (or a legally acceptable representative) can decline to continue receiving IP and/or other protocol-required therapies or procedures at any time during the study but continue participation in the study. If this occurs, the investigator is to discuss with the subject the appropriate processes for discontinuation from IP or other protocol-required therapies and must discuss with the subject the options for continuation of the Schedule of Assessments (Table 4) and collection of data, including endpoints and adverse events. The investigator must document the change to the Schedule of Assessments (Table 4) and the level of follow-up that is agreed to by the subject (eg, in person, by telephone/mail, through family/friends, in correspondence/communication with other physicians, from review of the medical records).

Withdrawal of consent for a study means that the subject does not wish to receive further protocol-required therapies or procedures, and the subject does not wish to or is unable to continue further study participation. Subject data up to withdrawal of consent will be included in the analysis of the study, and where permitted, publicly available data can be included after withdrawal of consent. The investigator is to discuss with the subject appropriate procedures for withdrawal from the study.

#### 8.1 Investigator or Sponsor Decision to Withdraw or Terminate Subjects' Participation Prior to Study Completion

The investigator and/or sponsor can decide to withdraw a subject(s) from IP, protocol procedures, or the study as a whole at any time prior to study completion.

Subjects may be eligible for continued treatment with Amgen IP(s) and/or other protocol-required therapies by a separate protocol or as provided for by the local country's regulatory mechanism, based on parameters consistent with Section 12.1.

# 8.2 Reasons for Removal From Study

# 8.2.1 Reasons for Removal From Treatment

Reasons for removal from protocol-required IP(s) or procedural assessments include any of the following:

- subject request
- safety concern (eg, due to an adverse event, protocol deviation, non-compliance, requirement for alternative therapy, pregnancy)
- protocol-specified criteria (eg, renal transplant, parathyroidectomy)
- death
- lost to follow-up
- decision by sponsor (other than subject request, safety concern, lost to follow-up)

#### 8.2.2 Reasons for Removal From Study

Reasons for removal of a subject from the study are:

- decision by sponsor
- withdrawal of consent from study
- death
- lost to follow-up

# 9. SAFETY DATA COLLECTION, RECORDING, AND REPORTING

9.1 Adverse Events

# 9.1.1 Definition of Adverse Events

An adverse event is defined as any untoward medical occurrence in a clinical trial subject. The event does not necessarily have a causal relationship with study treatment. The investigator is responsible for ensuring that any adverse events observed by the investigator or reported by the subject are recorded in the subject's medical record.

The definition of adverse events includes worsening of a pre-existing medical condition. Worsening indicates that the pre-existing medical condition (eg, diabetes, migraine headaches, gout) has increased in severity, frequency, and/or duration, and/or has an association with a significantly worse outcome. A pre-existing condition that has not worsened during the study or involves an intervention such as elective cosmetic surgery or a medical procedure while on study is not considered an adverse event.

CONFIDENTIAL

Page 56 of 79

If the toxicity grade of an adverse event worsens from the date of onset to the date of resolution, record as a single event with the worst CTCAE grade on the Adverse Event Summary eCRF.

The investigator's clinical judgment is used to determine whether a subject is to be removed from treatment due to an adverse event. In the event a subject, or subject's legally acceptable representative requests to withdraw from protocol-required therapies or the study due to an adverse event, refer to Section 6.3.1 for additional instructions on the procedures recommended for safe withdrawal from protocol-required therapies or the study.

# 9.1.2 Definition of Serious Adverse Events

A serious adverse event is defined as an adverse event that meets at least 1 of the following serious criteria:

- fatal
- life threatening (places the subject at immediate risk of death)
- requires in-patient hospitalization or prolongation of existing hospitalization
- · results in persistent or significant disability/incapacity
- congenital anomaly/birth defect
- · other medically important serious event

An adverse event would meet the criterion of "requires hospitalization", if the event necessitated an admission to a health care facility (eg, overnight stay).

If an investigator considers an event to be clinically important, but it does not meet any of the serious criteria, the event could be classified as a serious adverse event under the criterion of "other medically important serious event". Examples of such events could include allergic bronchospasm, convulsions, blood dyscrasias, DILI (see Appendix A for drug-induced liver injury reporting criteria), or events that necessitate an emergency room visit, outpatient surgery, or urgent intervention.

#### 9.2 Reporting of Adverse Events

Ongoing adverse events and serious adverse events in studies 20130356 or 20110100, will be entered as a concurrent condition on the Medical History eCRF.

# 9.2.1 Reporting Procedures for Adverse Events That do not Meet Serious Criteria

The investigator is responsible for ensuring that all adverse events observed by the investigator or reported by the subject that occur from the date of the first dose and up to

CONFIDENTIAL

Page 57 of 79

30 days after the last dose of IP, are reported using the applicable eCRF (eg, Adverse

Event Summary).

The investigator must assign the following adverse event attributes:

- adverse event diagnosis or syndrome(s), if known (if not known, signs or symptoms),
- dates of onset and resolution (if resolved),
- toxicity,
- assessment of relatedness toIP, and
- action taken.

The adverse event grading scale used will be the Common Terminology Criteria for Adverse Events (CTCAE, v4.0). The grading scale used in this study is described in Appendix A. The investigator must assess whether the adverse event is possibly related to the IP. This relationship is indicated by a "yes" or "no" response to the question: Is there a reasonable possibility that the event may have been caused by the IP?

The investigator is responsible for reviewing laboratory test results and determining whether an abnormal value in an individual study subject represents a clinically significant change from the subject's baseline values. In general, abnormal laboratory findings without clinical significance (based on the investigator's judgment) are not to be recorded as adverse events. However, laboratory value changes that require treatment or adjustment in current therapy are considered adverse events. Where applicable, clinical sequelae (not the laboratory abnormality) are to be recorded as the adverse event.

The Investigator is expected to follow reported adverse events until stabilization or reversibility.

#### 9.2.2 Reporting Procedures for Serious Adverse Events

The investigator is responsible for ensuring that all serious adverse events observed by the investigator or reported by the subject that occur from the date of the first dose through 30 days after the last day of the dosing interval of IP or end of study visit (whichever is later) are recorded in the subject's medical record and are submitted to Amgen. All serious adverse events must be submitted to Amgen within 24 hours following the investigator's knowledge of the event via the serious adverse event form.

After the protocol-required reporting period defined above, the investigator does not need to actively monitor subjects for serious adverse events. However, if the

AMGEN

Page 58 of 79

investigator becomes aware of a serious adverse event after this protocol-required reporting period, the investigator will report the event to Amgen within 24 hours following the investigator's knowledge of the event. Serious adverse events reported outside of the protocol-required reporting period will be captured within the safety database as clinical trial cases for the purposes of expedited reporting.

See Appendix A for a sample of the Serious Adverse Event Worksheet.

The investigator must assess whether the serious adverse event is possibly related to any study-mandated activity or procedure. This relationship is indicated by a "yes" or "no" response to the question: "Is there a reasonable possibility that the event may have been caused by a study activity/procedure"?

The investigator is expected to follow reported serious adverse events until stabilization or reversibility.

New information relating to a previously reported serious adverse event must be submitted to Amgen. All new information for serious adverse events must be sent to Amgen within 24 hours following knowledge of the new information. The investigator may be asked to provide additional follow-up information, which may include a discharge summary or extracts from the medical record. Information provided about the serious adverse event must be consistent with that recorded on the applicable eCRF (eg, Adverse Event Summary eCRF).

If a subject is permanently withdrawn from protocol-required therapies because of a serious adverse event, this information must be submitted to Amgen.

Amgen will report serious adverse events and/or suspected unexpected serious adverse reactions as required to regulatory authorities, investigators/institutions, and IRBs/IECs in compliance with all reporting requirements according to local regulations and good clinical practice.

The investigator is to notify the appropriate IRB/IEC of serious adverse events occurring at the site and other adverse event reports received from Amgen, in accordance with local procedures and statutes.

# 9.3 Pregnancy and Lactation Reporting

If a pregnancy occurs in a female subject, or female partner of a male subject, while the subject is taking protocol-required therapy, report the pregnancy to Amgen as specified below.

Page 60 of 79

In addition to reporting any pregnancies occurring during the study, investigators should monitor for pregnancies that occur after the last dose of cinacalcet through 90 days.

The pregnancy should be reported to Amgen's Global Patient Safety within 24 hours of the investigator's knowledge of the event of a pregnancy. Report a pregnancy on the Pregnancy Notification Worksheet (Appendix C). Amgen Global Patient Safety will seek to follow the pregnant woman throughout her pregnancy and her baby up to 12 months after birth.

If a lactation case occurs while the female subject is taking cinacalcet report the lactation case to Amgen as specified below.

In addition to reporting a lactation case during the study, investigators should monitor for lactation cases that occur after the last dose of cinacalcet through 90 days.

Any lactation case should be reported to Amgen's Global Patient Safety within 24 hours of the investigator's knowledge of event. Report a lactation case on the Lactation Notification Worksheet (Appendix C).

#### 10. STATISTICAL CONSIDERATIONS

#### 10.1 Study Endpoints, Analysis Sets, and Covariates

#### 10.1.1 Study Endpoints

#### **Primary Endpoint:**

Incidence of treatment emergent adverse events of interest

#### Secondary Endpoints:

#### 20140159 study only

- Achievement of ≥ 30% reduction from baseline to mean iPTH during weeks 11 and 15 (SOC arm of Study 20130356 only)
- Achievement of ≥ 30% reduction from baseline to mean iPTH during weeks 23 and 28 (SOC arm of Study 20130356 only)
- Percent change from baseline to mean iPTH during weeks 23 and 28 (SOC arm of Study 20130356 only)
- Change in corrected total serum calcium from baseline to mean value during weeks 23 and 28
- Change in serum phosphorus from baseline to mean value during weeks 23 and 28
- Achievement of a mean iPTH ≤ 300 pg/mL during weeks 23 and 28
- Serum cCa at baseline, week 11, and week 28
- Serum phosphorus at baseline, week 11, and week 28

#### Combined 20130356, 20110100, and 20140159 Studies

- Achievement of ≥ 30% reduction from day 1 of cinacalcet treatment to mean iPTH during weeks 11 and 15
- Achievement of ≥ 30% reduction from day 1 of cinacalcet treatment to mean iPTH during weeks 23 and 28
- Percent change in iPTH over time from day 1 of cinacalcet treatment
- Change in serum cCa over time from day 1 of cinacalcet treatment
- · Change in serum phosphorus over time from day 1 of cinacalcet treatment

#### **Exploratory Endpoints:**

#### Study 20140159 only

- · Growth velocity from baseline to EOS
- Change in Tanner stage from baseline to EOS

#### Combined Studies 20130356, 20110100, and 20140159

- Growth velocity from day 1 of cinacalcet treatment to EOS
- Change in Tanner stage from day 1 of cinacalcet treatment to EOS

#### Safety Endpoints:

- Nature, frequency, and severity of all adverse events
- Blood pressure, heart rate, and changes in laboratory parameters, including clinical chemistry and hematology

#### 10.1.2 Analysis Sets

#### Full Analysis Set

The Full Analysis Set (FAS) includes all enrolled subjects in Study 20140159.

#### Safety Analysis Set

The Safety Analysis Set includes all enrolled subjects who receive at least one dose of cinacalcet.

#### Efficacy Analysis Set

The Efficacy Analysis Set includes all enrolled subjects who received at least one dose of cinacalcet and have at least one assessment after day 1.

# 10.1.3 Covariates and Subgroups

The primary, secondary, and safety endpoints may be summarized by baseline age group (6 to < 12 years and 12 to < 18 years for Study 20130356; 28 days to < 2 years and 2 to < 6 years for Study 20110100) as supportive analyses upon availability of data in each subgroup.

This is an extension study of Studies 20130356 and 20110100. The sample size may be up to 78 subjects.

# 10.3 Planned Analyses

# 10.3.1 Interim Analysis

Several interim analyses may be conducted. The first interim analysis will be performed to support the Supplemental New Drug Application (sNDA) for pediatric indication. Its scope of analysis will be limited to the planned analysis using 20140159 study data only. The rest of interim analyses may be performed to support further request from regulatory. The scope of these analyses will be specified in a separate statistical analysis plan of interim analysis. There is no plan to conduct formal statistical testing. There are no plans to change the conduct of the study based on interim analysis results.

# 10.3.2 Primary Analysis

The general approach is to provide estimates for the primary and secondary endpoints for the study population.

The primary analysis of all endpoints will be conducted after all subjects have completed the week 32 EOS visit or terminated early from Study 20140159.

The primary analysis of all endpoints will be conducted after all subjects have completed the week 32 EOS visit or terminated early from Study 20140159.

# 10.4 Planned Methods of Analysis

# 10.4.1 General Considerations

There is no formal statistical testing for this study. The analysis for all endpoints will be descriptive in nature. Descriptive statistics will be used to summarize data for continuous variables (including n, mean, standard deviation (SD) or standard error (SE), median, 25th (Q1) and 75th (Q3) percentiles, and minimum and maximum values, where applicable).

For categorical variables, the number and percentage of subjects in each category will be reported. Graphical presentations may be provided for selected variables.

All summary tables will be provided by study treatment group: Study 20130356 (SOC, SOC + cinacalcet) and Study 20110100 and overall, unless otherwise specified.

# 10.4.2 Primary Endpoint

The analysis of the primary endpoint will be based on the Safety Analysis Set. The primary analysis of the primary endpoint is subject incidence of events of interest (EOI;

CONFIDENTIAL

# Page 62 of 79

AMGEN

Page 63 of 79

eg, hypocalcemia, convulsions, hypotension, worsening of heart failure, hypersensitivity, ischemic heart disease, QT prolongation/ventricular tachyarrhythmias, fracture, acute pancreatitis, drug-related hepatic disorders, nervous system disorders [excluding seizures], neoplastic events, and infection) for data in the 20140159 study only. The secondary analysis of the primary endpoint is the incidence of events of interest adjusted by the amount of safety follow-up time for combined data from parent studies and data from the 20140159 study. The 95% confidence intervals (CI) of the overall incidence rates will be reported.

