##### Events of interest (EOI)

The EOI names and search scopes (provided by Amgen Global Safety) are listed below:

EOI Name	Scope
Acute pancreatitis (SMQ)	Narrow
Cardiac failure (SMQ)	Narrow
Convulsions (SMQ)	Broad
Drug related hepatic disorders - comprehensive search (SMQ)	Narrow
Fractures (Amgen MedDRA Search Strategy)	Narrow
Hypersensitivity (SMQ)	Narrow
Hypocalcemia (Amgen MedDRA Search Strategy)	Narrow
Hypotension (Amgen MedDRA Search Strategy)	Narrow
Ischaemic heart disease (SMQ)	Narrow
Malignant or unspecified tumors (SMQ)	Narrow
Medication errors (SMQ)	Broad
Product use issues (MedDRA HLGT)	Broad
Nervous system disorders excluding seizures (Amgen MedDRA Search Strategy)	Broad
Torsade de pointes/QT prolongation (SMQ)	Narrow
Ventricular tachyarrhythmias (SMQ)	Narrow

Change from **studybaseline**

For each subject, change from **study** baseline for a given variable at a given time point or periods is defined as:

$$(\text{Value at the given time point or period} - \text{study baseline value})$$

and will be calculated at the same number of decimal places as the raw data provided by laboratory where applicable.

Percent change from **studybaseline**

For each subject, percent change from **study** baseline in a given variable at a given time point is defined as:

$$100 \times ((\text{value at the given time point or period} - \text{study baseline value}) / \text{study baseline value})$$

and will be calculated to one decimal place.

Change from day 1 of cinacalcet treatment

For each subject, change from baseline at first cinacalcet dose for a given variable at a given time point or period is defined as:

$$(\text{Value at the given time point or period} - \text{baseline at first cinacalcet dose})$$

and will be calculated at the same number of decimal places as the raw data provided by laboratory where applicable.

Percent change from day 1 of cinacalcet treatment

For each subject, percent change from baseline at first cinacalcet dose in a given variable at a given time point or period is defined as:

$$100 \times ((\text{value at the given time point or period} - \text{baseline at first cinacalcet dose}) / \text{baseline at first cinacalcet dose})$$

and will be calculated to one decimal place.

Growth velocity

Linear growth velocity (cm/year) =  $52 \times \text{change in height (cm)} / \text{number of weeks}$   
between the two assessments.

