#### **10.5 Analysis of Primary Endpoint**

The primary endpoint is incidence of treatment emergent adverse events of interest as defined in **Section 6.4**. The analysis will be based on Safety Analysis Set. Subject incidence of EOIs will be summarized by EOI category and **preferred term for data in Study 20140159 only for both the interim and final analyses. The 95% confidence intervals (CI) of the overall subject incidence rates will be reported.**

**The secondary analysis of the primary endpoint is follow-up time adjusted incidence of EOIs for combined data from parent studies and data from the 20140159 study for the final analysis.**

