##### **20140159studyonly**

An overall summary of treatment-emergent adverse events, **defined for study 20140159 only in section 6.4**, by toxicity grade and type will be provided.

Subject incidence of all treatment-emergent AEs, serious AEs, treatment-related, serious treatment-related AEs, AEs leading to withdrawal of investigational product, and fatal AEs will be tabulated by system organ class in alphabetical order and preferred term in descending order of frequency.

Subject incidence of AEs will be summarized for all treatment-emergent AEs, serious AEs, and EOIs by preferred term in descending order of frequency.

Subgroup analyses **of age groups** will be presented by system organ class in **alphabetical order** and preferred term in descending order of frequency if there are more than 4 subjects in each subgroup.

Treatment-emergent AEs will be listed for subjects who experienced QTcB  $\geq$  500 msec on study.

Focused adverse events questionnaires were administered for events of hypocalcemia, seizure, and infection, of which subject incidence will also be summarized.

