**Combined20130356, 20140159and20110100studies**

**Subject follow-up time adjusted incidence of all treatment-emergent AEs and EOIs, defined for studies 20130356, 20140159 and 20110100 combined in section 6.4, will also be tabulated by preferred term in descending order of follow-up time adjusted incidence rates for all subjects.**

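### The protocol names infection as a primary-endpoint event of interest, but the SAP table that defines that endpoint has no infection search and gives no reason

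*Protocol*

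**What the plan says.** Protocol 10.4.2 sets the primary analysis as the subject incidence of EOIs in the Safety Analysis Set. It illustrates the EOIs with a list introduced by 'eg', which finishes "nervous system disorders [excluding seizures], neoplastic events, and infection) for data in the 20140159 study only". A secondary analysis adjusts EOI incidence for follow-up time in the data combined with the parent studies.

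SAP 10.5 takes over the endpoint: "The primary endpoint is incidence of treatment emergent adverse events of interest as defined in" Section 6.4. That section holds a fixed table, introduced by "The EOI names and search scopes (provided by Amgen Global Safety) are listed below". It has 15 rows, and infection is not among them. SAP 10.5 then says "Subject incidence of EOIs will be summarized by EOI category and" preferred term, at both interim and final analysis, and adds: "The 95% confidence intervals (CI) of the overall subject incidence rates will be reported".

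The EOI set is used again in SAP 10.7.1. For Study 20140159 alone: "Subject incidence of AEs will be summarized for all treatment-emergent AEs, serious AEs, and EOIs by preferred term in descending order of frequency". For the combined studies, the tables cover "Subject follow-up time adjusted incidence of all treatment-emergent AEs and EOIs".

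The only place the SAP names infection is in SAP 10.7.1, where incidence from the focused questionnaires on hypocalcemia, seizure and infection is to be summarized as general safety output.

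**The concern.** This is a descriptive study whose primary endpoint is the incidence of EOIs, so the list of EOIs is the content of that endpoint. The protocol gives infection as an example of an EOI; the SAP's definition does not include it and does not say why.

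Infection is not a marginal item in this protocol. Protocol 7.3.10 has targeted questions on three event types at each study visit: hypocalcemia, seizures and infections. The first two have a row in the SAP table (Hypocalcemia, Convulsions). Infection does not.

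A reader of the primary EOI table, including the interim version that supports the sNDA, could not tell whether infection was left out on purpose or by oversight. If a total for any EOI is shown, a subject whose only EOI is an infection would be counted as having had none.

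**Working it through.** The plan states no figure to reproduce. The check is a line-by-line match of the two lists, followed by a search for any text that would reconcile them.

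**Step 1: match the lists.**

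| Protocol 10.4.2 | SAP 6.4 row(s) |
|---|---|
| Hypocalcemia | Hypocalcemia |
| Convulsions | Convulsions |
| Hypotension | Hypotension |
| Worsening of heart failure | Cardiac failure |
| Hypersensitivity | Hypersensitivity |
| Ischemic heart disease | Ischaemic heart disease |
| QT prolongation/ventricular tachyarrhythmias | Torsade de pointes/QT prolongation; Ventricular tachyarrhythmias |
| Fracture | Fractures |
| Acute pancreatitis | Acute pancreatitis |
| Drug-related hepatic disorders | Drug related hepatic disorders |
| Nervous system disorders (no seizures) | Nervous system disorders excluding seizures |
| Neoplastic events | Malignant or unspecified tumors |
| Infection | none |
| not named | Medication errors |
| not named | Product use issues |

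Protocol types with a row: 12 of 13. SAP rows used: 11 types × 1 row + 1 type × 2 rows = 13. Rows with no named protocol type: 2. Check: 13 + 2 = 15.

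**Step 2: can differing document versions explain it?** The SAP is dated 24 May 2016 and says it implements protocol amendment 3 of 16 March 2016. The superseding protocol of 1 June 2016 describes text changes only in 10.4.4, and its 10.4.2 still names infection. Version drift is not the explanation.

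**Step 3: where infection drops out.**
- The primary EOI table by category (SAP 10.5, interim and final).
- The EOI table by preferred term (SAP 10.7.1, Study 20140159).
- The EOI set in the combined follow-up-adjusted analysis (SAP 10.5 and 10.7.1).
- Any total for any EOI, if one is produced, and its 95% CI if that is what the word overall refers to in SAP 10.5. The wording does not settle this.

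**Step 4: where infection is kept.**
- For Study 20140159, all treatment-emergent events, along with other classes down to "fatal AEs will be tabulated by system organ class in alphabetical order and preferred term in descending order of frequency", on the same Safety Analysis Set.
- The questionnaire-based incidence (SAP 10.7.1).
- In the combined data, individual infection terms in the adjusted table of all treatment-emergent events. Protocol 10.4.4 also plans combined safety summaries.

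**Step 5: size, if a total for any EOI is reported.** Each subject whose only EOI is an infection lowers the total by 1/N:
- N = 78 (planned, SAP 3.2): 1/78 = 1.28, about 1.3 percentage points.
- N = 40 (assumed, to show a smaller dosed set): 1/40 = 2.5 percentage points.

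The documents do not say how many such subjects to expect, so the total effect cannot be calculated.

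**The case against.** The best case for leaving the plan alone has four parts.

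First, the endpoint itself is only the incidence of EOIs. The protocol's list is introduced by 'eg', and it is the SAP's job to supply the detail. That makes this an undocumented operational choice rather than a strict contradiction. The 'eg' does allow additions, which is why the medication-error and product-use rows are not criticised here. It does not explain why a type the protocol gives as an example of an EOI is not one in the SAP.

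Second, the fix would largely repeat a planned output. If the search were a whole system organ class, the new Study 20140159 row would carry the number already planned for that class, on the same analysis set and with the same definition of treatment emergence. This is right, and it limits the harm: nothing is lost from reporting. But those tables are general safety output and are not the primary endpoint.

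Third, a total for any EOI is never specified. Elsewhere in both documents, overall usually means pooled across parent-study groups. That is a fair reading, so the 1/N figures are conditional and the point does not rest on them.

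Fourth, matching by name involves judgement: malignant or unspecified tumors sounds narrower than neoplastic events. That stands, but neoplastic events at least has a counterpart. Infection has no counterpart of any width.

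**Conclusion.** The concern holds. The SAP's definition of the primary endpoint departs from the protocol on one expressly named event type out of 13, without explanation, and nothing else in either document repairs it. It should be put right before the analyses are run.

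The consequence is moderate. The primary EOI table and the other EOI-based outputs would omit infection, while infection data remain in the general tables. There is no hypothesis test to affect, and no change in study conduct depends on interim results. The SAP does not clearly promise a grouped adjusted combined rate or a category-level confidence interval for any EOI, so neither is counted as lost.

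The conclusion rests on reading the SAP 6.4 table as complete, as its lead-in and the pointer from SAP 10.5 imply. The effect of 1.3 percentage points per subject (2.5 at an assumed 40 dosed subjects) applies only if a total for any EOI is reported.

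**What to change.** Add an infection row to the SAP 6.4 table with a stated MedDRA search and scope. The Infections and infestations system organ class is one example; the choice belongs with the sponsor's safety group, which supplied the other searches. Infection then enters the SAP 10.5 primary analysis and the combined EOI analysis in the same way as the other EOIs.

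If the omission is deliberate, give the reason in SAP 6.4 and align protocol 10.4.2. The medication-error and product-use rows need no change.

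The cost is one table row and one search on adverse events that are coded in any case, or one sentence of explanation plus the protocol alignment. No new data collection is needed.
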